7.5 Reporting of Pregnancy

Although not an AE in and of itself, pregnancy as well as its outcome must be documented via the ***Pregnancy Report Form provided in the SRM***. Any pregnancy occurring in a participant or participant's partner from the time of consent to 30 days after the last dose of IP must be reported and then followed for outcome. Newborn infants born to the subject or subject's partner should be followed until 30 days old.

A FCBP must discontinue SL-172154 immediately if they become pregnant during the study. To ensure subject safety, each pregnancy must be reported to the Sponsor within two weeks of learning of its occurrence. The pregnancy must be followed to determine outcome (including premature termination) and status of mother and child. Pregnancy complications and elective terminations for medical reasons must be reported as a SAE. Spontaneous abortions must be reported as a SAE.

Any SAE occurring in association with a pregnancy brought to the investigator's attention after the subject has discontinued SL-172154 must be promptly reported to the Sponsor.

7.6 Reporting of Overdose

The following events should also be reported to the Sponsor and PrimeVigilance *within 24 hours*:

- Overdose: An overdose of SL-172154 should be reported within 24 hours to the Sponsor
- Suspected transmission of an infectious agent due to contamination of drug product
- Other events related to misuse of IP

7.7 Study Halting Rules

Administration of IP will be halted if a fatal SAE is reported to the Sponsor related to SL-172154. The Sponsor will inform the investigators immediately if such an event is reported and screening and enrollment will stop accepting new study subjects. The Sponsor will convene an ad hoc meeting of the SMC to review the SAE and overall safety profile and provide recommendations. The study Sponsor will inform the regulatory authorities (i.e., FDA) of the temporary halt and the disposition of the study.

7.8 Safety Oversight

An SMC will be implemented in this study and will consist of investigators and Sponsor representatives. SMC meetings will be conducted monthly (or more frequently if required) during dose escalation provided subjects have been enrolled and data are available to be reviewed. The SMC will operate in accordance with the SMC charter which will define roles and accountabilities and the process for safety review.

Throughout the conduct of the study, safety data will be reviewed for each subject on an ongoing basis. Additionally, periodic safety reviews will be undertaken by the SMC. Based on the severity of the DLTs, indicators of potential anti-tumor activity, and other factors, a recommendation on whether to modify the dose and/or study design; or continue enrollment will be made by the Sponsor collaboratively with input from the SMC. Regulatory authorities and IRBs/IECs will be notified of any decisions to prematurely halt the study or subject enrollment. (See section [14.1](#) for details on safety meetings).

8. ANTI-TUMOR ACTIVITY ASSESSMENTS

Although the clinical benefit of SL-172154 has not yet been established, the intent of offering this IP is to provide a possible therapeutic benefit, and thus the participant will be carefully monitored for tumor response and symptom relief in addition to safety and tolerability. Tumor response will be defined by RECIST v1.1 criteria according to the schedule outlined in the SOA. All participants who underwent the first disease assessment at the 6-week time point or progress or die before to the first disease assessment will be considered evaluable for response.

Assessments must be performed on a calendar schedule and should not be affected by dose interruptions or delays. Refer to the SOA (Section [6](#)) for the schedule of response assessments. More frequent response assessments may be performed at the discretion of the investigator. If study treatment is withdrawn for reasons other than disease progression, response assessments should continue as per the SOA until documented disease progression, the start of new anti-cancer therapy, withdrawal of consent or death. See Sections [8.2](#) for criteria for continuing treatment past disease progression.

8.1 Response Assessment

The same method of assessment and the same technique should be used to characterize each identified and reported lesion at baseline, on-treatment and during follow-up.

Tumor lesions will only be considered measurable by clinical examination when they are superficial and dimensions are accurately assessed using calipers or a ruler (e.g., skin nodules). For skin lesions, documentation by color photography including a ruler to estimate the size of the lesion, is required at all timepoints. Investigators will also provide a clinical description of the externally visible target lesion(s) at baseline and at each tumor assessment, as well as comments on any changes in the lesion(s) since the previous assessment. **Please refer to the Site Imaging Manual for complete instructions.** When lesions can be evaluated by both clinical examination and imaging, imaging evaluation should be undertaken since it is more objective. Furthermore, radiologic imaging will be essential in the evaluation of tumor lesions that have subdermal components that cannot be adequately assessed by digital medical photography.

All subjects will undergo radiologic imaging studies, preferably by contrasted CT scan, of the chest, abdomen and pelvis and all other sites of known disease at baseline and at the following intervals until disease progression: every 6 weeks until week 54 and every 12 weeks thereafter until year 2 and every 24 weeks until study conclusion. PET-CT, MRI, and/or bone scan should be performed as clinically indicated. In the event of a CR or PR, confirmatory scans should be performed in at least 4 weeks (>28 days) and preferably at the next disease assessment that is approximately 6 weeks later. Contrast enhanced imaging is required unless the subject is precluded from receiving contrast (e.g., hypersensitivity, renal impairment). If biopsies and scans for response assessment are to be performed on the same lesion, biopsies should always be performed after response assessments so that biopsy associated trauma or swelling does not confound response assessment.

All copies of scans and digital photographs taken for response assessment should be collected and stored at the site. The Sponsor may request that all of these images be sent to a designated central imaging vendor for collection, storage and possible future central re-analysis. Images may be used to assess the local and anesthetic or bystander response to therapy.

Treatment beyond progression will be permitted provided the subject meets protocol specified criteria in Section 8.2. If subjects discontinue investigational therapy prior to PD, they should continue to be followed with radiologic assessments until disease progression, start of a new anti-cancer therapy, withdrawal of consent or death.

8.1.1 Assessment of Response

Investigator-assessed response and progression will be evaluated in this study using RECIST v1.1 [Eisenhauer, 2009] (Section 16.5). Response of target and non-target lesions will be collected and analyzed by their injected or non-injected status in order to determine if anesthetic or bystander responses are observed.

Regarding target lesion selection, when more than one measurable tumor lesion is present at baseline, all lesions up to a maximum of 10 lesions in total, representative of all involved organs, should be identified as target lesions and recorded and measured at baseline. Target lesion selection will not be capped at a maximum of 2 lesions per organ e.g., if there are 3 cutaneous/subcutaneous measurable lesions, all 3 lesions can be selected as target lesions.

Given the relatively high rate of secondary primary malignancies in subjects with CSCC, new lesions must be carefully assessed to determine if they represent a second primary. A new CSCC will be considered as PD if the lesion is > 5 mm, can be clearly documented as not being previously present, and cannot be managed with standard therapy (such as surgical excision or topical palliation). Biopsy may be clinically indicated to confirm CSCC prior to determination of PD.

8.2 Criteria for Treatment Beyond Initial Progression

Subjects will be permitted to continue IP beyond initial PD provided the subject does not have clinical symptoms of progression, is tolerating IP, has experienced no decline in their ECOG performance status, and is gaining clinical benefit as assessed by the investigator. The subject

must be made aware of the potential benefits and risks of continuing the IP in the setting of PD by providing a separate written informed consent.

The subject may continue to be treated until one of the following criteria is met:

- Develops clinical symptoms or signs such that the benefit-risk ratio of continuing therapy is no longer justified
- Meets any of the criteria for discontinuation of IP (see Section [3.7](#))
- Experiences rapid PD with risk to vital organs or critical anatomical sites requiring urgent medical intervention

9. DATA ANALYSIS AND STATISTICAL CONSIDERATIONS

9.1 Study Design and Sample Size Determinations

The dose escalation will utilize a mTPI-2 design [\[Guo, 2017\]](#) with target DLT rate of 30% for the MTD. The DLT evaluable population is defined in section [9.2.1](#).

The mTPI-2 design employs a simple Beta-Binomial Bayesian model with decision rules based on the unit probability mass from the posterior probability of DLT rate. With the target DLT rate of 30%, the posterior probability of DLT rate unit interval (0, 1) is divided into subintervals with equal length of 0.1 that correspond to different dose escalation decisions: subinterval of (0.25, 0.35) is to stay at the current dose, subintervals below 0.25 is to escalate to next higher dose, and subintervals above 0.35 is to de-escalate to the next lower dose. Subjects will be enrolled in cohorts of approximately 3 subjects during the dose escalation. After each cohort of approximately 3 subjects, the posterior unit probability for subintervals will be calculated based on a noninformative prior distribution for the DLT rate (Beta (1,1)) and the total number of subjects with DLTs and DLT evaluable subjects for the current dose. A dose escalation/stay/de-escalation decision that corresponds to the subinterval with the highest unit probability mass will be selected. A minimum of 3 DLT evaluable subjects will be enrolled to a dose level and evaluated for DLT before a dose escalation/stay/de-escalation decision can be made unless unacceptable toxicity is observed prior to the enrollment of 3 subjects e.g., two subjects experience DLT before the third subject enrolls. A dose level will be considered unsafe, with unacceptable toxicity and no additional subjects enrolled at that dose level and above, if it has an estimated 95% or more probability of exceeding the target DLT rate of 30%. The maximum number of subjects evaluated for DLT for each dose level will be 12 subjects (about 4 cohorts of 3 subjects) if the dose escalation decision is to stay at the current dose from the first 3 cohorts. Based on the above design, the dose escalation decision rules are as the following for each dose level:

- When the number of DLT evaluable subject is <12 subjects:
 - Dose escalate if the observed DLT rate <25%;
 - Stay at the current dose if the observed DLT rate between 25%-33%;
 - Dose de-escalate if the observed DLT rate >33%;
- After reaching the maximum 12 subjects, the dose escalation decision will be either escalate or de-escalate as the following:
 - Dose escalate if the observed DLT rate $\leq 25\%$;
 - Dose de-escalate if the observed DLT rate $\geq 33\%$;

See [Table 5](#) for dose escalation decision rules based on the total number of subjects evaluable for DLT and the number of DLTs observed.

Table 5: Dose Escalation Decision Rules for Each Dose Level based on mTPI-2

Number of subjects with DLTs	Number of Subjects									
	3	4	5	6	7	8	9	10	11	12
0	E	E	E	E	E	E	E	E	E	E
1	S	S	E	E	E	E	E	E	E	E
2	D	D	D	S	S	S	E	E	E	E
3	DU	DU	D	D	D	D	S	S	S	E
4	.	DU	DU	DU	D	D	D	D	D	D
5	.	.	DU	DU	DU	DU	DU	D	D	D
6	.	.	.	DU	DU	DU	DU	DU	DU	D
7	DU	DU	DU	DU	DU	DU
8	DU	DU	DU	DU	DU
E = escalate to the next higher dose level					S = stay at the current dose level					
D = de-escalate to the next lower dose level					DU = de-escalate to the next lower dose level and current dose level will never be used again due to unacceptable toxicity					

Note: For each dose level, a minimum of 3 subjects will be enrolled and evaluated before a dose escalation/stay/de-escalation decision can be made unless unacceptable toxicity is observed prior to the enrollment of 3 subjects e.g., 2 subjects experience DLT before the third subject enrolls.

Sample Size Determination:

The planned sample size is approximately 18 subjects. This sample size assumes evaluation of four dose levels with approximately 12 subjects treated in the dose escalation cohorts and approximately 6 subjects in the pharmacodynamic cohort. The goal is to enroll approximately 6 subjects at the potential RP2D, including subjects in dose escalation and the pharmacodynamic cohort. In dose escalation cohorts, subject may be replaced if not DLT evaluable.

NOTE: The planned sample sizes may be revised if additional dose levels are evaluated or if more subjects (i.e., 4 subjects dosed in a cohort to ensure that at least 3 subjects are DLT evaluable) are enrolled. The Sponsor, in consultation with the SMC, may also elect to add subjects to the dose escalation if additional data are needed for RP2D determination.

9.2 Statistical Analyses

Complete details of the statistical analysis will be provided in the Statistical Analysis Plan (SAP). Any deviations from, or additions to, the original analysis plan described in this protocol will be documented in the SAP and final study report.

9.2.1 Analysis Populations

For the analysis, the following populations are defined:

Population	Description
Enrolled	All subjects who have signed the main study informed consent form (ICF).
Screen Failures	All subjects who have signed the main study ICF but have not received any study treatment.
All Treated	All subjects who have received at least one dose of IP. Safety data will be evaluated based on this population.
DLT Evaluable	All treated subjects 1) who have received ≥ 2 of the 3 scheduled doses of IP during cycle 1 and complete the safety follow-up through the 21-day DLT evaluation period; or 2) who experience any DLT during the DLT evaluation period. DLT evaluable subjects will be used to guide dose escalation and to determine the MTD or MAD.
Response Evaluable	Subjects in the All Treated Population who have a baseline disease assessment and have at least one post-baseline disease assessment or have progressed or died before the first post-baseline disease assessment.
Pharmacokinetic	Subjects in All Treated Population from whom at least one PK sample is obtained and analyzed. The PK population will be used for the PK analysis.
Pharmacodynamic	Subjects in the All Treated Population for whom at least one pharmacodynamic sample is obtained and analyzed. The pharmacodynamic population will be used for the pharmacodynamic data analysis.

9.2.2 Interim Analyses

During dose escalation, the number of subjects with DLTs will be determined after each cohort of approximately 3 subjects has been evaluated for DLT. The summary of DLTs for each dose level will be based on the number of subjects with DLTs from all subjects dosed and evaluated at the corresponding dose level who meet the definition of the DLT Evaluable Population. Selected AE summary tables and listings may be provided during dose escalation to support dose escalation decisions.

9.2.3 General Data Analysis Consideration

Tabular summaries will be presented by dose levels/cohorts and total number of subjects in the corresponding population. Categorical data will be summarized by the number and percentage of subjects in each category. Continuous variables will be summarized by descriptive statistics. As it is anticipated that accrual will be spread thinly across centers and summaries of data by center would be unlikely to provide valuable information, data from all participating centers will be

pooled prior to analysis. All data up to the time of study completion/withdrawal from study will be included in the analysis for each subject, regardless of duration of treatment.

9.2.4 Safety Analyses

The safety evaluation will be based on the All Treated Population and the DLT evaluation will be based on the DLT evaluable population. DLTs will be summarized by dose level. Frequency tables will be used to describe safety and tolerability parameters AEs, irAEs, SAEs, fatal SAEs and AEs leading to discontinuation of SL-172154. Changes in toxicity grade for clinical chemistry and hematology will be summarized. Change from baseline QTcF will also be summarized. Graphs may also be presented where appropriate. AEs will be mapped to a Medical Dictionary for Regulatory Activities (MedDRA) preferred term and system organ classification. Laboratory abnormalities will be graded according to the NCI CTCTAE v5., if applicable. Concomitant medications will be coded using the World Health Organization Drug Dictionary.

MTD: The MTD will be estimated using isotonic regression (based on the DLTs observed in DLT evaluable subjects). Specifically, the MTD is the dose for which the isotonic estimate of the DLT rate is closest to the target DLT rate of 30%. If two or more doses tie for the smallest difference, perform the following rules:

- If the estimated DLT rate < 30% for all doses, then select the higher dose among the tied doses;
- If the estimated DLT rate for the tied doses are a combination of < 30% for and > 30%, then select the higher dose among the tied doses;
- If the estimated DLT rate > 30% for all dose, then select the lower dose among the tied doses.

A MAD will be reported if the observed DLT rate is <25% among all dose levels. Otherwise, an MTD will be reported.

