16. APPENDICES

16.1 mTPI-2 Dose Escalation Scenarios

See [Table 5](#) in Section [9.1](#) for dose escalation decision rules based on the total number of subjects evaluable for DLT and the number of DLTs observed.

For each dose level, subjects will be enrolled in cohorts of approximately 3 to evaluate DLT and make a dose escalation/stay/de-escalation decision based on decision rules in [Table 5](#) in Section [9.1](#) as the following steps:

- **Step 1:** The first cohort of at least 3 subjects will be enrolled and evaluated for DLT, and dose escalation/stay/de-escalation decision will be made among at least 3 DLT evaluable subjects. Assuming 3 subjects are DLT evaluable in cohort #1, the following decisions will be made based on the number of subjects with a DLT among the 3 DLT evaluable subjects:
 - If no subject with a DLT, dose escalate to the next higher dose level;
 - If 1/3 subject with a DLT, stay at the current dose level and move to step 2;
 - If 2/3 subjects with a DLT, dose de-escalate to next lower dose level;
 - If 3/3 subjects with a DLT, dose de-escalate to next lower dose level and the current dose level will never be used;
 - If the first 2 subjects experience a DLT before the third subject enrolls, then de-escalate to the next lower dose level and the current dose level will never be used.
- **Step 2:** As there is 1 subject with DLT among 3 DLT evaluable subjects in cohort #1, approximately 3 subjects will be enrolled and evaluated for DLT at the current dose in cohort #2. Assuming 3 DLT evaluable subjects in cohort #2, the following decisions will be made based on the number of subjects with DLT among the 6 DLT evaluable subjects from cohort #1 and cohort #2:
 - If 1/6 subjects with a DLT (no subject with a DLT in cohort #2), then dose escalate to the next higher dose level;
 - If 2/6 subjects with a DLT (1 subject with a DLT in cohort #2), stay at the current dose level and move to step 3;
 - If 3/6 subjects with a DLT (2 subjects with a DLT in cohort #2), dose de-escalate to next lower dose level;
 - If 4/6 subjects with a DLT (3 subjects with a DLT in cohort #2), dose de-escalate to next lower dose level and the current dose level will never be used.

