- **Step 3:** As there are 2 subjects with DLT among 6 DLT evaluable subjects in cohort #1 and #2, approximately 3 subjects will be enrolled and evaluated for DLT at the current dose in cohort #3. Assuming 3 DLT evaluable subjects in cohort #3, the following decisions will be made based on the number of subjects with DLT among the 9 DLT evaluable subjects from cohort #1, cohort #2 and cohort #3:

- If 2/9 subjects with a DLT (no subject with a DLT in cohort #3), then dose escalate to the next higher dose level;
- If 3/9 subjects with a DLT (1 subject with a DLT in cohort #3), stay at the current dose level and move to step 4;
- If 4/9 subjects with a DLT (2 subjects with a DLT in cohort #3), dose de-escalate to next lower dose level;
- If 5/9 subjects with a DLT (3 subjects with a DLT in cohort #3), dose de-escalate to next lower dose level and the current dose level will never be used.

- **Step 4:** As there are 3 subjects with DLT among 9 DLT evaluable subjects in the first 3 cohorts, approximately 3 subjects will be enrolled and evaluated for DLT at the current dose in cohort #4. Assuming 3 DLT evaluable subjects in cohort #4, the following decisions will be made based on the number of subjects with DLT among the 12 DLT evaluable subjects from all 4 cohorts:
 - If 3/12 subjects with a DLT (no subject with a DLT in cohort #4) with 25% DLT rate, then dose escalate to the next higher dose level;
 - If 4-6 subjects with a DLT (1-3 subjects with a DLT in cohort #4) with 33% to 50% DLT rate, dose de-escalate to next lower dose level.

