3.2 Statistical Design for Dose Escalation

The dose escalation will utilize a mTPI-2 design with target DLT rate of 30% for the MTD. The mTPI-2 design employs a simple Beta-Binomial Bayesian model with decision rules based on the unit probability mass from the posterior probability of DLT rate. With the target DLT rate of 30%, the posterior probability of DLT rate unit interval (0, 1) is divided into subintervals with equal length of 0.1 that correspond to different dose escalation decisions: subinterval of (0.25, 0.35) is to stay at the current dose, subintervals below 0.25 is to escalate to next higher dose, and subintervals above 0.35 is to de-escalate to the next lower dose. Subjects will be enrolled in cohorts of approximately 3 subjects during the dose escalation. After each cohort of approximately 3 subjects, the posterior unit probability for subintervals will be calculated based on a noninformative prior distribution for the DLT rate (Beta(1,1)) and the total number of subjects with DLTs and DLT evaluable subjects for the current dose. A dose escalation/stay/de-escalation decision that corresponds to the subinterval with the highest unit probability mass will be selected. A minimum of 3 DLT evaluable subjects will be enrolled to a dose level and evaluated for DLT before a dose escalation/stay/de-escalation decision can be made unless unacceptable toxicity is observed prior to the enrollment of 3 subjects e.g., two subjects experience DLT before the third subject enrolls. A dose level will be considered unsafe, with unacceptable toxicity and no additional subjects enrolled at that dose level and above, if it has an estimated 95% or greater probability of exceeding the target DLT rate of 30%. The maximum number of subjects evaluated for DLT for each dose level will be 12 subjects (about 4 cohorts of 3 subjects) if the dose escalation decision is to stay at the current dose from the first 3 cohorts.

Based on the above design, the dose escalation decision rules are as the following for each dose level:

- When the number of DLT evaluable subject is <12 subjects:
 - Dose escalate if the observed DLT rate <25%;

- Stay at the current dose if the observed DLT rate between 25%-33%;
- Dose de-escalate if the observed DLT rate $>33\%$;
- After reaching the maximum 12 subjects, the dose escalation decision will be either escalate or de-escalate as follows:
 - Dose escalate if the observed DLT rate $\leq 25\%$;

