8.1 Maximum Tolerated Dose Evaluation

The Maximum Tolerated Dose (MTD) evaluation will be based on the DLT Evaluable Population. The number and percentage of subjects with DLT will be presented by dose level for dose escalation cohorts. The MTD level will be indicated in the summary.

The MTD will be estimated using isotonic regression (based on the DLTs observed in the DLT evaluable subjects). A MAD will be reported if the DLT rate never reaches $\geq 25\%$. Otherwise, an MTD will be reported. Isotonic regression is a way to estimate the MTD under the assumption that toxicity increases with dose. When using isotonic regression, the first step is to identify the doses where the dose-toxicity monotonicity assumption is violated. The DLT estimate is then adjusted for the violators such that the final estimate of the DLT rate increases with the dose. The target DLT rate is then used to select the MTD. For example, suppose that when the trial is completed, the observed DLT rates [<# subjects who experienced DLT]/[# evaluable subjects] at five dose levels are (0/3, 1/3, 0/3, 4/15, 2/4). In this example the observed DLT rate at Dose Level 2 (i.e., 1/3=33%) is higher than the observed DLT rate at Dose Level 3 (i.e., 0/3=0%). To adjust for this violation, the DLT estimates are replaced with their average, i.e., $(1/3+0/3)/2=1/6$, resulting in the isotonic regression DLT estimates (0/3, 1/6, 1/6, 4/15, 2/4) = (0%, 16.7%, 16.7%, 26.7%, 50%), which monotonically increases with the dose level. Based on this isotonic estimate, assuming that the trial goal is to find the dose with the DLT rate of 30%, Dose Level 4 will be selected as the MTD. If there are no violators of the dose-toxicity monotonicity assumption, isotonic regression directly uses the observed DLT rates as the final estimates for MTD selection. For subjects who undergo intra-subject dose escalation, only DLTs that occur during the DLT period on the subject's initial dose level the assignment will be used for MTD determination.

In the case of dose levels with estimated toxicity of equal distance (tied dose levels) from the target toxicity of 30%, the following approach will be used: among all tied dose levels the highest dose level with target toxicity $\leq 30\%$ will be selected, unless all tied dose levels have estimated toxicity $> 30\%$, in which case the lowest dose level will be selected.

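### The MTD rule does not exclude doses the design has closed as unsafe, so a closed dose can be reported as the MTD; the protocol and SAP also differ on ties that straddle 30%

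*Protocol*

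**What the plan says.** **Closure.** Protocol 9.1 treats a dose as unsafe, with "no additional subjects enrolled at that dose level and above, if it has an estimated 95% or more probability" of exceeding the 30% target. SAP 3.2 uses the same limit: "if it has an estimated 95% or greater probability of exceeding the target DLT rate of 30" percent. Table 5 of the protocol defines the code DU by saying that the "current dose level will never be used again due to unacceptable toxicity". Appendix 16.1 works through examples. Step 1 has "If 3/3 subjects with a DLT, dose de-escalate to next lower dose level and the current dose level will never be used", and Step 3 gives the same consequence for 5 DLTs in 9 subjects.

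**MTD selection.** Protocol 9.2.4 states: "Specifically, the MTD is the dose for which the isotonic estimate of the DLT rate is closest to the target DLT rate of 30" percent. SAP 8.1 also fits an isotonic regression and selects by distance from the 30% target. Both documents report a MAD only if no observed rate reaches 25%. For every other case SAP 8.1 says "Otherwise, an MTD will be reported", and protocol 9.2.4 does the same. SAP 8.1 adds, for the DLT summary, "The MTD level will be indicated in the summary".

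**Ties.** If tied doses lie on both sides of 30%, protocol 9.2.4 takes the higher dose. SAP 8.1 takes the highest tied dose at or below 30%, which is the lower of a straddling pair.

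**The concern.** The closure rule and the MTD rule are written independently. Closure governs enrolment, and no sentence in protocol 9.2.4 or SAP 8.1 carries it into MTD selection. Selection is by absolute distance from 30%. A dose far above target can therefore beat a dose with no DLTs, and if it is the only dose tested it wins by default. There is no provision for reporting that no MTD was found.

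Identifying the MTD or MAD is a primary objective. A programmer who follows SAP 8.1 literally could label as maximum tolerated a dose that the trial's own rule calls unsafe. The tie conflict is a second, smaller inconsistency in the same paragraphs. Protocol 9.2 says departures from the protocol analysis will be documented in the SAP and final report; SAP 8.1 does not flag this one.

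**Working it through.** **Inputs from the documents.** Target 30%, Beta(1,1) prior, closure at 95%, Table 5, at most 12 evaluable subjects per dose, cohorts of about 3 (protocol 9.1); four dose levels and about 12 escalation subjects (protocol 3.2.1). The documents give no expected DLT rates, so all true-rate curves below are assumptions.

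**Reproducing Table 5.** With r DLTs in n subjects, the posterior is Beta(r+1, n−r+1). Closure requires P(p > 0.30) ≥ 0.95. Every DU cell agrees. Of 75 cells, 73 follow directly from the model. The other two (3/12 and 4/12) follow the stated rule that forces escalation or de-escalation at 12 subjects.

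| Result | P(p > 0.30) | Distance from 30% |
|---|---|---|
| 3/3 | 0.992 | 0.700 |
| 4/6 | 0.971 | 0.367 |
| 5/9 | 0.953 | 0.256 |
| 6/10 | 0.978 | 0.300 |

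**Closed dose above a clean dose.** Level 1 is 0/3 (escalate). Level 2 goes 1/3 (stay), 2/6 (stay), 5/9 (DU). That is 3 + 9 = 12 subjects. The isotonic estimates are 0 and 0.556. The distances are |0 − 0.30| = 0.300 and |0.556 − 0.30| = 0.256, so level 2 is the MTD under both documents. In general, a closed dose beats a dose with 0 DLTs whenever its rate is below 60%.

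**Lowest dose closed.** Level 1 at 3/3, 4/6 or 5/9 is the only estimate, so it is the MTD. Alternatively, level 1 is 0/3, level 2 is 2/3 (de-escalate), and level 1 then goes to 2/6 and 5/9 (DU). The distances are 0.256 for level 1 and 0.367 for level 2, so closed level 1 is the MTD. The same holds with level 2 at 3/3.

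**Pooling.** With 1/9, 5/9 (DU) and 5/12, levels 2 and 3 pool to 10/21 = 0.476. The distance is 0.176, against 0.189 for level 1. This needs 30 subjects.

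**Frequency at planned size.** All paths were enumerated exactly with cohorts of 3, 12 subjects, closure applied, and the trial stopping on a de-escalation order at level 1 (the documents do not say what that order means). There are 65 final tables; 26 contain a closed dose, and 6 name it as MTD under both tie rules. The six are those described above. One can be checked by hand. For true rates 5/45/60/70%, the path 0/3 then 5/9 has probability 0.95³ × (3 × 0.45 × 0.55²)² × 0.45³ = 0.8574 × 0.1668 × 0.0911 = 1.30%. The other five tables bring it to 1.32%.

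| Assumed true DLT rates (%) | Closed dose named MTD | Level 1 closed |
|---|---|---|
| 2/5/10/20 | 0.001% | 0.001% |
| 5/15/30/45 | 0.05% | 0.01% |
| 10/25/40/55 | 0.33% | 0.1% |
| 5/45/60/70 | 1.3% | 0.01% |
| 2/50/60/70 | 1.7% | under 0.01% |
| 20/35/50/60 | 1.7% | 1.2% |
| 30/45/60/70 | 5.0% | 4.5% |
| 50/60/70/80 | 19.5% | 19.3% |

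If enrolment continued at level 1 after a de-escalation order there, the last three rows would be 3.5%, 13.3% and 55.7%. With 18 to 48 escalation subjects, which protocol 9.1 permits but does not plan, the two steep curves (5/45/60/70 and 2/50/60/70) give about 8–14%, and 5/15/30/45 gives 0.9–1.3%.

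**Ties.** A straddling tie needs two estimates that sum to 0.60. No unpooled pair with 3, 6, 9 or 12 subjects per dose does this. Across 3 to 12 subjects per dose, 29 pairs do, and each involves a dose with 5 or 10 subjects. For 0/3 and 3/5 the protocol names the 60% dose and the SAP the 0% dose. For 0/3 and 6/10 the protocol names a closed dose and the SAP does not. With cohorts of exactly 3, the documents differ in none of the trials at 12 or 18 subjects and in at most 0.02% at 24 to 48.

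**The case against.** Read as a whole, the plan hardly invites anyone to call a closed dose tolerated: it labels such a dose unsafe and says it will not be used again. SAP 8.1 prints DLT counts beside the label, so 3/3 or 5/9 would be visible. The RP2D rests on the totality of the data, not on this label. Five of the six tables are closures of the starting dose, and the sixth rests on 5/9, which only just crosses the limit. Protocol 3.3 expects little systemic toxicity at the starting dose. Even the top planned dose, 0.1 mg or about 0.0014 mg/kg at 70 kg, is about 70-fold below the IV starting dose of 0.1 mg/kg. The steep curves have no basis in the documents. Intermediate doses, or one DLT in a further cohort at level 1 (1/6, distance 0.133), would change the answer. The tie conflict is almost inert.

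Most of this stands as a limit on frequency, and the RP2D point limits the consequences. It does not remove the gap. The closure text concerns enrolment and use of the dose, the MTD text never refers to it, and literal application gives the wrong label. Closure exists for unexpectedly toxic doses, which is where the error concentrates.

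**Conclusion.** The concern holds and should be fixed. As written, both documents can report a closed dose as the MTD, and they conflict on straddling ties.

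At the planned 12 escalation subjects the first problem is rare on gentle curves, between 1% and 2% on steep ones, and 5% or more only if the starting dose has a true DLT rate of 30% or above. These figures depend on the assumed curves, cohorts of 3 and the stopping convention. The tie conflict is real in the text and negligible with cohorts of exactly 3; cohorts of other sizes, replacement or early stopping can produce it.

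No subject's dosing is affected, because closure already bars enrolment and SAP section 1 records that enrolment was discontinued. That updated SAP kept the rule, so what remains is reporting on a primary objective. The documents do not say whether any dose was closed or any tie occurred.

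**What to change.** In SAP 8.1, and in protocol 9.2.4 if it is amended, reconcile MTD selection with the closure rule. One way is to limit the isotonic candidates to doses that are not DU and lie below any DU dose, and to report 'no MTD identified' if none remains. Reconcile the two straddling-tie rules into one text, and record the change in the SAP as protocol 9.2 provides.

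The cost is two or three sentences, with two consequences. No MTD is reported when the lowest dose is closed; the last column of the frequency table shows how often. With 0/3 below a closed dose, the 0/3 dose, 30 points from target, becomes the only candidate, so the text should say how that result is labelled.
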